Cardiometabolic Benefits of Potatoes Mediated Along the Gut-Vessel Axis in Adults with Metabolic Syndrome

I. Objectives

The *objective of this application* is to establish evidence that incorporation of potatoes into a diet pattern based on the *Dietary Guidelines for Americans (DGA)* enhances cardiometabolic health in persons with metabolic syndrome (MetS) by improving microbiota- and host-mediated metabolic responses along the gut-vessel axis. Our central hypothesis is that the inclusion of potatoes, as part of a *DGA*-based dietary pattern, will potentiate gut barrier function and attenuate postprandial hyperglycemia (PPH)-mediated impairments in vascular endothelial function (VEF). To test this, we will complete the following objectives: 1) define changes in gut barrier function in association with improved gut microbiota composition, increased fecal short chain fatty acid (SCFA) production, and decreased serum endotoxin, 2) define changes in postprandial glycemic responses and endotoxemia, and 3) define changes in gut hormones that promote glycemic control and changes in markers of oxidative stress in relation to improvements in endothelial vascular function, all following 2-week potato consumption. Upon completing this study, we anticipate novel evidence demonstrating gut-level benefits of a potato-containing diet to lower cardiometabolic risk in MetS adults.

II. Procedures

A. Study Design

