We will enroll equal numbers of male and female MetS adults ($n = 30$; 18-50 y) from the Columbus, OH area as we detailed¹ to complete a 2-arm, randomized controlled, cross-over trial. Participants will be randomized in 3-unit blocks to receive a *DGA*-based diet containing Russet Burbank potatoes (350 g/d; 260 kcal; 12.4 g resistant starch) or an energy-matched bagel that is nearly devoid of resistant starch. Our approach closely follows recommendations of the *DGA*² and entails high scientific rigor by providing all foods during each 14-d intervention. On day 0, 7, and 14 of each period, coinciding with when participants obtain prescribed foods, we will assess anthropometrics (weight, height, waist circumference) and blood pressure. At baseline (day 0) of each trial, fasting glucose, insulin, and endotoxin will be measured to verify stable health status. Following each 14-d intervention, participants will provide a fecal sample and undergo testing in the fasted state for metabolic endpoints, gut barrier function, and VEF. Then, they will receive a glucose challenge (75 g) to examine VEF in relation to PPH at 30 min intervals for 2 h. Gut permeability probes (sucralose, erythritol, lactulose, mannitol) will also be co-administered on day 14, and urine collected for 24-h. After completing a 2-wk washout period (i.e. to restore microbiota composition³), participants will receive the alternate treatment (i.e. *DGA* diet + potato or bagel) and repeat all procedures.

B. Study Subjects

Enrollment Criteria. MetS adults will be studied because of their impaired VEF in association with glucose intolerance.⁴ We will enroll those who are unmanaged (i.e. no drug therapy) and they will be required to meet these established MetS criteria⁵ to improve homogeneity of study outcomes: i) fasting glucose 100-126 mg/dL, ii) waist circumference >102 cm for men or >88 cm for women, and iii) fasting triglyceride >150 mg/dL. We anticipate that they may also fulfill other MetS criteria, specifically HDL-C (<40 mg/dL for men, <50 mg/dL for women) and elevated blood pressure⁶ (>120/80 mmHg); these will be considered for co-variate analysis. Other inclusion criteria are: i) non-smoker, ii) non-dietary supplement user (>1-mo), iii) free of gastrointestinal disorders, CVD,

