cancer, and iv) no recent use of antibiotics, or any medications affecting glycemia, lipidemia, or blood pressure. Participants having any of these ***exclusion criteria*** will not be enrolled: i) use of anti-inflammatory agents or probiotics, ii) vegetarian, gluten intolerant, carbohydrate-restricted diet, iii) alcohol intake >2 drinks/d, or iv) ≥ 7 h/wk of aerobic activity.

Power Calculation. Plasma glucose and FMD during the 2-h postprandial period ($AUC_{0-120\text{ min}}$) and fasting endotoxin following 14-d controlled feeding have been selected as the **primary outcome variables**. These endpoints had no gender differences ($P>0.05$) in our prior studies. PPH was also inversely related ($P<0.001$) to FMD.^{4,7} MetS adults had improved FMD following low-fat milk ingestion compared with rice milk ($AUC_{0-3\text{ h}}: 1150\pm145$ vs 908 ± 118 , CV=56%) and attenuated PPH.⁴ For this study, we predict that FMD_{AUC} will be 25% greater in DGA+Potato during the oral glucose challenge on day 14. Thus, 26 MetS subjects would be needed to detect a treatment effect with >80% power ($P<0.05$). We will therefore enroll 30 subjects to account for unexpected attrition and increase power. A similar power calculation was performed using endotoxin measured from MetS vs. healthy adults.¹ To detect a 25% predicted lowering of endotoxin, 22 MetS subjects would be needed. Based on our preliminary data, DGA+Potato could lower endotoxin by increasing vitamin C status in addition to alleviating gut dysbiosis in a resistant starch-dependent manner. This secondary hypothesis will be tested by measuring vitamin C on day 14 using our routine HPLC-ECD method.¹

Statistical Analysis Plan

Most data in will be analyzed by linear mixed effects models (LMMs) with random effect for subjects (to account for repeated measures) and fixed effects for gender, time period, and their interactions. Multivariate regression analysis will define pairwise correlations between study variables in the presence or absence of potential study covariates. Statistical significance for all analyses will be set at $P<0.05$.

C. Detailed Study Procedures

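### The regression for pairwise correlations names no unit of analysis and no subject, diet or period term, so it allows repeated readings to be pooled as if independent

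*Combined protocol and SAP*

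**What the plan says.** The Statistical Analysis Plan (section II.B) has three sentences.

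- The first sends most of the data to mixed models with a "random effect for subjects (to account for repeated measures" and with "fixed effects for gender, time period, and their interactions".
- The second gives correlations to a different method: "Multivariate regression analysis will define pairwise correlations between study variables in the presence or absence of potential study covariates". It names no subject effect, no diet or period term, no clustered variance, and no statement of what one row of data is. The only covariates named in advance are HDL-C and blood pressure (section II.B, Enrollment Criteria).
- The third applies the 0.05 level to every analysis, so these correlations will be declared significant or not.

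Repeats per person are built into the design. After washout, "participants will receive the alternate treatment" and all procedures are repeated (section II.A). On day 14, blood markers and FMD are taken every 30 min for 2 h (section II.C, Test trials), and Sampling Handling counts five blood time points.

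Objective 1 concerns changes in gut barrier function in association with changes in microbiota, fecal short-chain fatty acids and endotoxin. Objective 3 concerns "changes in markers of oxidative stress in relation to improvements in endothelial vascular function".

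**The concern.** The mixed-model sentence shows that the authors know the data are clustered. The correlation sentence carries none of that over. Two things are at stake if rows are pooled.

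**Error rate.** Two readings from one person are not two independent observations. Counting them as such makes the standard error of a correlation too small.

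**What is estimated.** FMD and gut barrier function are scheduled only at the end of each 14-day period; day 0 blood work covers glucose, insulin and endotoxin. A person's change in FMD or barrier function can therefore only be a potato-versus-bagel contrast. A pooled correlation is a blend of three things: stable differences between people, any shift that diet causes in both variables, and the link between one person's changes. Only the last says whether the markers move together within a person.

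**Working it through.** The plan gives no figure for the correlation analysis. Its sample sizes (26 for FMD, 22 for endotoxin) concern other comparisons, so there is nothing of its own to reproduce here.

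**Inputs**
- People: 30 enrolled (Power Calculation).
- Rows per person, m: 2 with one value per visit; 10 if five readings (0, 30, 60, 90, 120 min) are used at both visits.
- Level: 0.05, taken as two-sided because the plan does not say.
- Intraclass correlation (ICC), the share of variance that lies between people: not in the documents. Range 0.3-0.7 assumed, equal in both variables.

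**Step 1: false positives from pooling, no true link.** The variance of the pooled correlation is inflated by about V = 1 + (m − 1) × ICCx × ICCy, and the rejection rate is 2 × [1 − Φ(1.96/√V)]. Example, m = 10 and ICC 0.5: V = 1 + 9 × 0.25 = 3.25; 1.96/1.803 = 1.087; rate 27.7%. Simulation (5,000 to 20,000 replicates) agrees.

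| Rows per person | ICC | V | Formula | Simulation |
|---|---|---|---|---|
| 2 | 0.3 | 1.09 | 6.0% | 5.7% |
| 2 | 0.5 | 1.25 | 8.0% | 7.8% |
| 2 | 0.7 | 1.49 | 10.8% | 11.0% |
| 10 | 0.3 | 1.81 | 14.5% | 14.8% |
| 10 | 0.5 | 3.25 | 27.7% | 28.5% |
| 10 | 0.7 | 5.41 | 39.9% | 41.2% |

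If either variable has ICC 0, V = 1 and there is no inflation.

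**Step 2: mixing of levels (ICC 0.5, no within-person link).**
- Between-person correlation of 0.5: pooled r is about 0.24, declared significant in 48% of trials (60 rows) or 91% (300 rows).
- Diet shifts both variables by 0.8 SD (assumed): 20% (60 rows) or 62% (300 rows).
- Diet shifts both by 0.45 SD: 8.7% or 31%, little above the 7.8% and 28.5% with no shift. The 0.45 is the plan's 25% FMD effect over its CV of 56% (0.25/0.56), if that CV describes single values.

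**Step 3: is a subject term enough?** No. With a subject term but no diet term, the 0.45 SD shifts give 14.3% (60 rows) or 38.2% (300 rows). Adding diet brings these to 5.1% and 4.9%. If both variables also follow the glucose-challenge time course, subject plus diet rejects 99% of the time; adding time gives 4.2%.

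**Step 4: one difference per person.** Correlating potato-minus-bagel differences rejected 4.8-5.5% of the time in every setting simulated.

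**Step 5: a model for the 30-min readings.** Five readings share one visit. With subject, diet, period and time but no visit effect, rejection is about 9-16% when visit-level variance is 0.2-0.3 of the total and subject variance 0.3-0.4 (assumed). With a visit-level term it returns to 5%.

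**Step 6: what the pairs can detect.** By Fisher's z at 80% power, r = tanh[(1.96 + 0.84)/√(n − 3)]. For n = 30: tanh(2.80/√27) = 0.49. For n = 26: tanh(2.80/√23) = 0.53. Period adjustment replaces n − 3 by n − 4 and gives 0.50 and 0.53.

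**The case against.** The strongest reply is that the sentence is silent, not wrong. It fixes no rows, and it rules out neither a subject term nor diet as a covariate. An analyst guided by the wording of objective 3 could correlate one change per person and keep the 5% level. This stands: a reader might infer that the plan commits to treating readings as independent, and the text does not say so. What remains is that analyses with very different error rates all fit the sentence, and nothing says which will be run.

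The reply on size also stands in part. Stool, 24-h urine permeability and fasting endotoxin give one value per visit, and two of the primary outcomes (glucose and FMD) are areas under the curve, so most correlations cannot have 10 rows per person. The 14-40% range applies only to time-point correlations of postprandial markers with FMD, which the plan neither announces nor excludes.

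A reader might also infer that these correlations are the only evidence on mechanism. They are not: the mixed models cover most of the data, and comparing a marker between diets is mechanism evidence too.

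Finally, the objectives' wording does not demand a within-person link alone, and a shift in both variables under potato is what the hypothesis predicts. That is fair. But the diet comparison of each variable already shows a shared shift; it does not show that people whose marker changed more also had a larger change in FMD. The plan should say which is meant.

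**Conclusion.** The concern holds as a gap in specification with a quantified risk. If readings are pooled, the nominal 5% test rejects about 6-11% of the time with one value per visit and about 14-40% with all time points, and it cannot separate the within-person link from between-person and diet effects. These rates rest on assumed ICCs of 0.3-0.7 in both variables and 30 people; they shrink to 5% if either ICC is zero. The inflation with one value per visit is modest, and the mixing of levels is the more serious defect there.

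It would be wrong to infer that the primary results are compromised. The diet comparisons of glucose AUC, FMD AUC and fasting endotoxin do not use this regression. The point should be settled before the codes are broken, but it does not threaten the main conclusions.

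**What to change.** Replace the correlation sentence with:

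> *Associations will be estimated on within-person DGA+Potato minus DGA+Bagel differences (one pair per person), adjusted for period. Any analysis of the 30-min readings will use a mixed model with random subject and random visit-within-subject effects and fixed diet, period and time, with the predictor centred within visit. These analyses are exploratory.*

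Period adjustment is needed because a common period shift enters the differences with opposite sign in the two sequences. The second analysis answers a different question, whether two variables track each other over the 2 h after glucose, and should be reported as such.

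The cost is SAP wording and slightly more analysis; data collection does not change. The drawback is about 26-30 independent pairs, so only correlations of about 0.49-0.53 or more are detectable with 80% power. That is what the design holds on this question; counting 60 or 300 rows would hide the limit without removing it.

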Throughout the span of the study (~8-12 weeks in duration depending on participant/investigator availability) which consists of four weeks total of controlled feeding, a blood collection at wk 0 and 2 and then repeated following a ≥ 2 week washout period, and 1 screening day, we will be collecting a total of ~210 mL or ~0.88 cups) of blood. Urine will be collected in provided containers (VWR) containing 10% thymol to inhibit bacterial growth. We will then have the participants return their urine samples to the study center or coordinate with study personnel to meet at a public and mutual location to return their samples within 24-h after collection. Feces will be collected using a commercial commode specimen collection system (Fisher Scientific). Briefly, the collection kit consists of the necessary materials (e.g. gloves, waste bag) for participants to easily and hygienically collect their stool without contaminating the sample or themselves. Volumes of urine will be recorded and fecal mass and observations will be recorded based on the Bristol Stool Chart.¹⁰

During each blood collection, plasma will be obtained by centrifugation and then transferred to cryogenic storage tubes. Serum samples will be obtained by allowing the blood to clot, followed by centrifugation and transfer to cryogenic storage tubes. Tubes will be stored at -80° C until analysis can be completed. Analyses will include plasma glucose, insulin, triglyceride, total cholesterol, nitrite, nitrate, arginine, ADMA, SDMA, MDA, CCK, serum endotoxin. Urine will be stored at -80°C until analysis can be completed. Analysis from urine will include sucralose and erythritol. Fecal samples will be stored at -80°C until analysis can be completed. Feces analysis will include microbiota composition and fecal short chain fatty acids (butyrate, acetate, propionate). Remaining plasma, serum, urine, and fecal samples not used for these analyses will be archived for 5 years at -80 C in the event we decide to measure additional inflammatory, antioxidant, or microbiota related markers. Appropriate notation has been made in the informed consent to alert participants that we will be archiving specimens and that they have the right to refuse our use of these specimens for future analyses. Lastly, approval from OSU IRB will be sought via a protocol amendment prior to the analysis of any additional biomarkers not specified herein.

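### The 0.05 rule covers an open set of pairwise correlations with no multiplicity control, list of pairs or exploratory label

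*Combined protocol and SAP*

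**What the plan says.** The Statistical Analysis Plan in section II.B has three sentences.

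- **Model.** "Most data in will be analyzed by linear mixed effects models". What falls outside "most" is not described.
- **Correlations.** "Multivariate regression analysis will define pairwise correlations between study variables in the presence or absence of potential study covariates". No pairs are listed, and no covariate set is fixed.
- **Threshold.** "Statistical significance for all analyses will be set at" P<0.05.

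The Power Calculation paragraph names three primary outcomes: "Plasma glucose and FMD during the 2-h postprandial period" (each as an area under the curve) "and fasting endotoxin following 14-d controlled feeding have been selected as the" primary variables. It also states one secondary hypothesis, on vitamin C.

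The Sampling Handling paragraph in section II.C gives the laboratory list: "Analyses will include plasma glucose, insulin, triglyceride, total cholesterol, nitrite, nitrate, arginine, ADMA, SDMA, MDA, CCK, serum endotoxin"; "Analysis from urine will include sucralose and erythritol"; and "Feces analysis will include microbiota composition and fecal short chain fatty acids", of which three are named.

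No section mentions an adjustment for multiple testing, an order of testing, a false discovery rate, an exploratory label or a method for the microbiota data.

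**The concern.** Section I makes association part of two objectives. Objective 1 ties gut barrier change to microbiota, short chain fatty acids and endotoxin. Objective 3 ties gut hormones and oxidative stress to vascular function. The pairwise regressions are the only stated analysis that links a gut variable to a vascular one.

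The family of correlations is open-ended, and each may be run with or without covariates. The only decision rule given is the one used for the primary outcomes. If raw P-values are compared with 0.05 across that family, some chance associations are likely to be reported as mechanism. A reader of the results could not tell a link predicted beforehand from one picked out of many.

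**Working it through.** The plan states no number of tests and no overall error rate, so there is no figure of its own to reproduce. The check counts the tests that its wording allows.

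**1. Count the named variables.**
- Blood: 12 (Sampling Handling).
- Urine: 2, sucralose and erythritol (Sampling Handling).
- Stool: 3 short chain fatty acids (Sampling Handling). Microbiota composition is left out because no number of features is given.
- FMD and vitamin C: 2 (Power Calculation).
- Total: 12 + 2 + 3 + 2 = 19.

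This leaves out blood pressure, anthropometrics, separate urine fractions and single postprandial time points.

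**2. Widest reading: every pair.**
- Pairs: 19 × 18 / 2 = 171.
- Expected false positives if all are null: 171 × 0.05 = 8.55. Dependence between tests does not change this expectation.
- If half are null: 85.5 × 0.05 = 4.3.
- Running each pair with and without covariates gives up to 342 tests, but the two runs of a pair are strongly dependent.

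**3. Narrow reading: gut-by-vessel pairs only.** The split is an assumption.
- Gut (7): sucralose, erythritol, butyrate, acetate, propionate, endotoxin, CCK.
- Vessel (7): FMD, nitrite, nitrate, arginine, ADMA, SDMA, MDA.
- Pairs: 7 × 7 = 49.
- Expected false positives if all are null: 49 × 0.05 = 2.45.
- If half are null: 24.5 × 0.05 = 1.2.
- Chance of at least one if all are null and the tests are independent: 1 − 0.95^49 = 0.919.

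**4. Allow for correlation among the variables.** This is a simulation of 10,000 trials with 30 independent observations each, two-sided tests, and no true gut-to-vessel association. Variables within each block share a common correlation, which is assumed.

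| Within-block correlation | Mean false positives | Chance of at least one | Same, with Benjamini-Hochberg at 5% |
|---|---|---|---|
| 0 | 2.43 | 92% | 4.8% |
| 0.3 | 2.47 | 86% | 5.1% |
| 0.6 | 2.48 | 65% | 4.0% |

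Correlation lowers the chance of any false finding but leaves the expected number at about 2.5. When false findings do occur, they come in clusters.

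**5. Taxa, only if tested singly.** With an assumed 10 to 200 taxa all null, the treatment comparison alone would add 10 × 0.05 = 0.5 to 200 × 0.05 = 10 expected false positives.

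**The case against.** Several points on the other side stand.

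- **Silence is not a rule against adjustment.** A reader might infer that the plan prescribes unadjusted P-values. It sets a threshold and does not say whether the P-values compared with it are raw or adjusted. The fault is an omission.
- **Taxon-level testing is not documented.** A reader might infer one test per taxon from the reference to microbiota composition. The documents never mention taxa, and a community-level analysis is not excluded.
- **The 171 pairs are not all gut-to-vessel links.** Many lie within one system (glucose with insulin, nitrite with nitrate, ADMA with SDMA) and are plausibly truly related. The plan does not say that every pair will be tested. The Power Calculation also reports an inverse relation between postprandial hyperglycemia and FMD in earlier work, so a complete null over all 171 is not credible. That pair is outside the 49, because glucose is not in the assumed split.
- **The axis claim does not rest on correlations alone.** Glucose, FMD and endotoxin are randomised comparisons that cover both ends of the axis, and objectives 1 and 3 each include one of them.

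It might also be said that mechanistic correlations are understood to be exploratory. The plan does not say so. It gives them the same threshold as the primary outcomes and writes associations into the objectives. The points above reduce the size of the problem but do not supply the missing rule.

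**Conclusion.** The concern holds as an omission. The correlation analyses have no multiplicity control, no list of pairs and no exploratory label, although two of the three objectives use them.

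For gut-to-vessel links, a fair size is about 2.5 expected false positives if all 49 pairs are null and about 1.2 if half are. The chance of at least one is 65% to 92% under the complete null. These figures rest on the assumed 7 × 7 split, within-block correlations from 0 to 0.6, raw P-values and 30 independent observations. The 8.55 figure is an upper case for the named variables, counting each pair once with every pair null. It is not a forecast.

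A reader might go further and conclude that false mechanistic findings are nearly certain. The documents do not support that: under strong correlation the chance for the gut-to-vessel set is 65%, and true associations would reduce the expected number. Near-certainty would need all 171 pairs to be null and nearly independent, or a large number of taxa that the plan does not state.

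This is a worthwhile, inexpensive improvement and does not threaten the randomised comparisons. The multiplicity of the three primary outcomes is a separate issue.

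**What to change.** Add the following to the Statistical Analysis Plan before the sample codes are broken.

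1. **Name the correlations that the hypothesis needs**, using measured variables. For example: FMD with glucose, MDA and ADMA; endotoxin with sucralose recovery, erythritol recovery, butyrate and vitamin C. For each, state whether the result with or without covariates is the one that counts. These seven at 0.05 each would give 7 × 0.05 = 0.35 expected false positives if all are null, and a 30% chance of at least one if independent (1 − 0.95^7). The plan should therefore also say whether they are adjusted among themselves.
2. **Apply Benjamini-Hochberg false discovery rate control to all remaining correlations** and label them exploratory. In the simulation above, this cut the chance of any false finding among 49 null pairs from 65–92% to 4–5%.
3. **If taxa are tested individually**, run one paired community-level permutation test first, then report taxa at a stated false discovery rate.

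The cost is some wording, a few lines of code and fewer nominally significant secondary findings. No extra participants, samples or visits are needed, and the primary outcome tests and their power are unchanged.

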If a participant is telephoned and is unavailable, a message will be left requesting a callback at a convenient time or that at a member of the study team will try calling again at a later time. No confidential or sensitive information will be shared with third parties or left on answering machines.

Intervention timeline. Each participant will complete a 2-arm (*DGA* + Potato; *DGA* + Bagel), randomized, cross-over study. For this study, each participant will visit the study center a total of 12 times (6 times per study arm, including 1) baseline measurements of anthropometrics, serum glucose, insulin, endotoxin, and pick-up of meals for days 1-3, 2) pick-up of meals for days 4-7 2) pick-up of meals for days 8-11 and measurement of anthropometrics, 3) pick-up of meals for days 11-14 and stool collection kit, 4) 2 h postprandial testing, and 5) return samples from 24-h urine collection. Interventions will be separated by two weeks (for women, interventions will be separated by 2, 6, 10 etc. weeks to ensure vascular testing will be performed at the same time of the menstrual cycle).

Baseline visit. On day 0 of each trial arm, participants will report in the fasted state (10-12 hours) to the study center for assessment of height, weight, waist circumference, blood pressure, serum glucose, serum insulin, and serum endotoxin. They will receive 3-4 days of *DGA* meals plus potatoes (350g/day) or bagels (1/day = 95g).

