Test trials. At the end of the intervention period (day 14), participants will report back to the laboratory in the fasted state (10-12 hours) for assessment of height, weight, waist circumference, blood pressure, serum glucose, serum insulin, and serum endotoxin. Participants will return a stool sample collected on day 13 of the intervention period at home. Participants will ingest a sugar solution containing 75 g glucose, which we and others have routinely shown to induce PPH, oxidative stress, and VED. This will be co-ingested with 1 g sucralose, 1 g erythritol, 1 g mannitol, 5 g lactulose for assessment of gut permeability. Then, at 30 min intervals during the 2 h postprandial period, we will assess blood markers and brachial artery flow-mediated dilation. During each study visit, participants will have access to drinking water and use of the restroom as needed. Urine will be collected during the 2 h postprandial period in the laboratory, and participants will be instructed on urine collection for when they return home following their laboratory visit. Participants will return to the study center the following day to drop off their 24-h urine collection containers. To ensure that the order by which each participant completes each trial is randomized, a random sequence generator (<http://www.random.org/sequences/>) will be used to determine the order by which each participant will undergo the two trials.

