Privacy/Confidentiality. For all data and records that are a part of this study, a number (i.e. code) will be assigned to each participant and will only be available to research personnel. Any records containing the names of participants will be stored in a locked filing cabinet or on a password protected computer in the PI's laboratory or office. Research personnel under the supervision of the PI and the PI himself will be the only individuals that have access to this information. The names of participants will not be used for publication in any form. The records will be maintained until the data are published, up to a maximum of five years. All archived samples will be coded, but the key linking the code to each participant's identifiable information will have been destroyed. In addition, participants will be instructed that their participation in this study is voluntary and that they may withdraw at any time without prejudice. Data (biochemical values) obtained from this study will be stored on a computer in the PI's laboratory. In addition, a backup of digital data will be stored on the

PI's computer in his office. Both computers are password protected and both doors are locked when work areas are not in use.

D. Internal Validity

For all data and records that are a part of this study, a number (i.e. code) will be assigned to each participant. This will minimize measurement bias when performing analysis on dietary records, and biochemical markers because all samples/records will be coded. The codes will only be broken once data analysis has been completed and verified by the PI.

F. Medical Safety Plan

All aspects of the clinical study will be conducted in [name] clinical lab located in [name]. Participants will be fasted for 10-12 hours prior to each study visit. We recognize that certain risks associated with fasting include: hypoglycemia, weakness, and fainting. This duration of fasting is consistent with guidelines set forth by the American Diabetes Association to minimize risk to the individual⁶² when determining fasting blood glucose concentrations.

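### Section D's participant-level code does not by itself conceal diet in a crossover, and no masking of FMD, a primary outcome, to diet or period is specified

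*Combined protocol and SAP*

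**What the plan says.** Power Calculation (II.B) lists the primary outcomes as "Plasma glucose and FMD during the 2-h postprandial period", each as AUC from 0 to 120 min, together with fasting endotoxin. The 26 subjects are justified on FMD AUC.

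Test trials (II.C) says that at 30-min intervals after the glucose drink "we will assess blood markers and brachial artery flow-mediated dilation". It does not say who acquires or reads FMD, or what that person knows.

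Internal Validity (II.D) contains three relevant statements:
- Scope of coding: "For all data and records that are a part of this study, a number (i.e. code) will be assigned to each participant".
- Stated benefit: "This will minimize measurement bias when performing analysis on dietary records, and biochemical markers because all samples/records will be coded".
- Code break: "The codes will only be broken once data analysis has been completed and verified by the PI".

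Privacy/Confidentiality (II.C) describes the code in nearly the same terms and adds that it "will only be available to research personnel". Outcome assessors are not excepted.

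The two diets differ visibly. The Baseline visit paragraph (II.C) has participants receive "meals plus potatoes (350g/day) or bagels (1/day = 95g", and meals are collected at the study center.

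**The concern.** A code limits measurement bias only if it hides the thing that could bias the reader. Here that is the diet that preceded the visit. In a parallel trial a bare participant number can do this, because each person has one treatment. In this crossover the same number covers a potato visit and a bagel visit. What must be hidden is which visit is which, and the plan describes no visit-level or treatment-level code.

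The gap matters most for FMD. The sentence on measurement bias does not mention it, and it carries the sample size. If whoever acquires or measures the recordings knows the diet, a tendency to favour one diet passes straight into the potato-bagel difference. Randomised order and within-person comparison do not remove an error that follows diet.

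**Working it through.** **1. Does the described code conceal diet?** Setting the sections side by side:

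| Question | What the plan gives |
|---|---|
| What is coded? | All data and records, so FMD records would carry a code too (II.D) |
| What does the code identify? | The participant: "a number (i.e. code) will be assigned to each participant" (II.D) |
| How many diets per participant? | Two, in random order (II.A; Test trials, II.C) |
| Who can see the code? | Research personnel, with no exception for assessors (Privacy/Confidentiality, II.C) |
| When is it broken? | After analysis (II.D) |
| Is FMD acquisition or reading masked to diet or period? | Not stated anywhere |

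Two recordings from one person share a code. The code therefore separates people but does not conceal diet within a person, and the within-person contrast is the one being tested. The late code break does not change this, because II.D does not say that the code carries diet or period.

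**2. The plan's own figure.** The plan gives N = 26 for a 25% effect, CV 56%, more than 80% power and P < 0.05. It does not give the within-person correlation ρ or the sidedness. For a paired t-test, with the effect and SD as fractions of the mean:

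SD_diff = 0.56 × √(2(1 − ρ)), d = 0.25 / SD_diff.

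Two-sided at 0.05, the N for 80% power is 81 at ρ = 0, 42 at ρ = 0.5, 26 at ρ = 0.70 and 18 at ρ = 0.8. So 26 can be neither confirmed nor refuted; it corresponds to ρ of about 0.70. This does not bear on the masking point and is used only to choose an SD below.

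**3. Illustration of what a diet-related bias would do.** These are assumptions, not figures from the plan:
- no true effect of diet on FMD AUC;
- a two-sided paired t-test at 0.05;
- SD_diff set to the value that gives 80% power at N = 26, where d = 0.572, so SD_diff = 0.25 / 0.572 = 0.437 of the mean;
- a bias b toward one diet, as a fraction of mean FMD AUC.

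The test statistic is then noncentral t with N − 1 degrees of freedom and noncentrality (b / SD_diff) × √N. At N = 26 and b = 0.05 this is (0.05 / 0.437) × √26 = 0.583. At b = 0.10 it is 1.167. The critical value is 2.060.

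| Bias b | False-positive rate, N = 26 | N = 30 |
|---|---|---|
| 2.5% | 0.059 | 0.061 |
| 5% | 0.087 | 0.093 |
| 10% | 0.202 | 0.228 |

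The result depends on the unstated correlation. At N = 26, with b = 5% and 10%, the rates are 0.072 and 0.141 at ρ = 0.5 (SD_diff = 0.560). At ρ = 0.8 (SD_diff = 0.354) they are 0.106 and 0.283.

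**The case against.** The best defence is that II.D codes everything, not just biochemistry, and holds the code until analysis is complete. That is right as far as it goes. A reader might infer that FMD falls outside the coding; it does not. Only the stated bias benefit is limited to dietary records and biochemical markers.

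A second defence is that a file labelled with participant and period does not reveal diet unless the reader also knows that person's sequence, because order is randomised. This also stands. The exposure comes from knowing the sequence or meeting the participant. But the plan does not say who holds the sequence or keep it from FMD staff, so the code alone cannot be relied on.

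Four stronger readings are tempting and are not supported:
- **That FMD is unmasked, or the trial open-label.** The documents are silent. They do not say what the FMD operator or reader knows, and masked reading may already be practice.
- **That the staff who hand out food also read FMD.** The Medical Safety Plan (II.F) has the same research-team members monitoring safety at every visit. It does not say who hands out meals or who reads FMD.
- **That a tiny shift in measured artery diameter would produce a set share of the planned effect.** The reference AUC of 908 over 3 h has no units, and no artery diameter is given. FMD is a relative change, so a shift common to baseline and peak nearly cancels. At an assumed 4 mm, 4.000 to 4.2016 mm is 0.2016 / 4.000 = 5.04%. Adding 0.017 mm to both gives 0.2016 / 4.017 = 5.02%.
- **That bias of any particular size is likely.** No figure in the documents tests this.

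**Conclusion.** The point holds as a gap in the stated method. The participant-level code does not by itself conceal diet in a crossover, and masking of FMD acquisition or reading to diet or period is not specified, although FMD AUC is a primary outcome and the basis for N = 26. The same limit applies to the blood, urine and stool measurements, for which coding is the only protection described.

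The size of any actual bias is unknown. On the assumptions above, a diet-related bias of 5% or 10% of mean FMD AUC would take a nominal 5% error rate at N = 26 to about 9% or 20%. Across correlations of 0.5 to 0.8 the ranges are about 7% to 11% and 14% to 28%. A bias of 2.5% would matter little (about 6%). The conclusion about masking rests on the text and does not depend on these figures. It does not change N.

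**What to change.** Amend II.D along these lines: *Stored FMD recordings will be measured under random visit-level IDs that hide participant, period and diet. The key will be kept from the reader until the FMD data set is locked. Blood, urine and stool samples will be labelled with visit-level random IDs in the same way.*

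State separately whether the FMD operator knows the diet. Masked reading does not remove bias that arises while the recording is being made. If masking the operator is not feasible, say so.

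The cost is some file and label handling by a current team member who does not read the files. This presumes that recordings are stored and that such a person is available, which the plan does not state. No additional visit or participant is needed. If recordings are already read without knowledge of diet, one sentence in II.D saying so settles the reading part for FMD.
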